9.6. Data management

Data retrieval and management will be conducted separately in each country. Investigators in each country will obtain all necessary permissions and prepare a data application to its country-specific data custodian. A data manager in each country will ensure correctness of the delivered raw data before data management start. Records (within each country) from different registries will be merged by unique personal identifier or its pseudonym and de-identified before the analysis. Data will be cleaned, and coded, and harmonised analytic datasets will be prepared according to the specifications provided in [Annex 3](#). All four countries use similar coding systems for medications, diagnoses and procedures, and codes will be shared whenever feasible. There may be slight between-country variations in the specific diagnostic or procedure codes, which will be addressed in consultation with clinicians on a country-specific basis. Patient level data are kept on secure servers within each respective country. Patient-level data from Finland, Norway, or Sweden will not be made available to researchers at the ‘vendor organizing institution’ (Aarhus University Hospital, Denmark) or the MAH (Pfizer).

For data management and analyses, SAS version 9.3 or later and/or R version 3.1.1 or later will be used.

9.7. Data analysis

For all data analyses, the birth (not the patient/mother) will be the unit of analysis. Given that a woman could have more than one birth during the study period, data analyses will account for correlated observations using GEE (generalized estimating equation) or robust variance estimates. All steps of the country-specific data analyses will be conducted separately in each participating country according to the description below. Each country will generate a set of identical analytic tables. Registry data will not be provided for very low numbers (less than 5 events) due to data security and data confidentiality rules.

After conducting the country-specific data analyses, country-specific datasets containing crude and adjusted estimates of association will be transferred to Aarhus University Hospital, Denmark, for meta-analyses.

Given that gabapentin has several indications and that administrative data available for this study have low sensitivity in identifying relevant indications for all pregnancies, in this study pregnancies exposed to gabapentin will be compared with pregnancies exposed to medications with similar sets of indications. Because confounding by indication or severity

of indication may persist even against an active comparator,⁷ the amount of confounding may be inferred indirectly by examining whether estimates of association differ depending on the comparator. Here, pregabalin and lamotrigine, which are both indicated for epilepsy, have been identified as suitable active comparators.

In a 2019 publication from Sweden, all individuals aged 15 years or older and being dispensed at least 2 prescriptions of gabapentin in the period 2006-2013 were identified (N=85,360).⁴⁹ The indication of use (i.e. health status before start of treatment) was 6.4% epilepsy, 20% psychiatric disorders, and 52.1% musculoskeletal disorders. In the same publication, the indication of use for pregabalin (n=120,664) was 5.4% epilepsy, 40.9% psychiatric disorders, and 46.2% musculoskeletal disorders. Published data on the most common gabapentin indication in pregnant women are unavailable at this time.

9.7.1. Calculation of prevalences of birth outcomes

Prevalence of each birth outcome will be computed as the number of newborns with a given outcome divided by the total number of newborns at risk. For the outcomes of congenital malformations and stillbirth in the analysis not including pregnancies ending in 2nd trimester abortion the number of newborns at risk will be the total number of live or stillbirths. For the outcomes of congenital malformations and stillbirth in the analysis including pregnancies ending in a 2nd trimester abortion the number of newborns at risk will be the number of live or stillbirths and the number of pregnancies ending in a 2nd trimester abortion. For all the other birth outcomes, the number of newborns at risk will be the number of liveborn newborns.

9.7.2. Calculation of incidence rates of postnatal outcomes

Incidence rate of each postnatal outcome will be computed as the number of first-recorded events during the follow-up divided by the total person-time at risk contributed by each livebirth. The follow-up for each newborn will begin on the date of birth and will end on the date of a given postnatal outcome, emigration, death, or the end of the observation period.

9.7.3. Estimation of prevalence ratios and hazard ratios

Crude and adjusted prevalence ratios and 95% Wald confidence intervals (CIs) for each birth outcome and a given population/contrast will be estimated using log-binomial regression.

Crude and adjusted incidence rate ratios and 95% Wald CIs will be estimated using Cox's proportional-hazards regression for each postnatal outcome. Crude and adjusted prevalence ratios and incidence rates ratios will be calculated for all pregnancies, including pregnancies with monotherapy exposure and pregnancies with polytherapy exposure, as well as the subset of only pregnancies with monotherapy exposure.

9.7.3.1. Computation of propensity scores

To account for confounding by all measured covariates, adjusted analysis will be conducted using propensity score (PS) stratification, following the approach by Paterno et al.⁵⁰ For each pregnancy, a PS will be computed, using logistic regression, as the probability being exposed

to gabapentin vs. given comparator conditional on the measured covariates listed in [Section 9.3.3](#) and [Annex 3](#).⁵¹

PS will be estimated for each birth using a generic-outcome model, meaning that all prespecified covariates will be included in the PS-estimating model, regardless of the association with the outcome. Wyss et al showed, in a simulation study, that such a model performs well when multiple outcomes are being examined;⁵² furthermore, it is reasonable to assume in this study that all confounders distort the association in the same direction for all outcomes. In case of model non-convergence, covariates with the smallest cell counts (corresponding to the lowest prevalence of covariates) will be removed one-by-one until convergence is achieved. Categories of variables with small cell counts may be collapsed if applicable by an analyst in each country.

A separate PS will be estimated for each study population and comparison. To summarise, the following sets of propensity scores will be estimated:

1. First-trimester gabapentin (monotherapy or polytherapy) vs. first-trimester unexposed to AEDs
2. First-trimester gabapentin (monotherapy or polytherapy) vs. first-trimester pregabalin (monotherapy or polytherapy)
3. First-trimester gabapentin (monotherapy or polytherapy) vs. first-trimester lamotrigine (monotherapy or polytherapy)
4. First-trimester gabapentin (monotherapy or polytherapy) vs. first-trimester pregabalin or lamotrigine (monotherapy or polytherapy)
5. First trimester gabapentin (monotherapy only) vs. first-trimester unexposed to AEDs
6. First trimester gabapentin (monotherapy only) vs. first-trimester pregabalin (monotherapy only)
7. First trimester gabapentin (monotherapy only) vs. first-trimester lamotrigine (monotherapy only)
8. First-trimester gabapentin (monotherapy only) vs. first-trimester pregabalin or lamotrigine (monotherapy only)
9. Any-trimester gabapentin (monotherapy or polytherapy) vs. any-trimester unexposed to AEDs
10. Any-trimester gabapentin (monotherapy or polytherapy) vs. any-trimester pregabalin (monotherapy or polytherapy)
11. Any-trimester gabapentin (monotherapy or polytherapy) vs. any-trimester lamotrigine (monotherapy or polytherapy)
12. Any-trimester gabapentin (monotherapy or polytherapy) vs. any-trimester pregabalin or lamotrigine (monotherapy or polytherapy)
13. Any-trimester gabapentin (monotherapy only) vs. unexposed to AEDs

14. Any-trimester gabapentin (monotherapy only) vs. any-trimester pregabalin (monotherapy only)
15. Any-trimester gabapentin (monotherapy only) vs. any-trimester lamotrigine (monotherapy only)
16. Any-trimester gabapentin (monotherapy only) vs. any-trimester pregabalin or lamotrigine (monotherapy only)

After estimation of each PS, the following steps will be taken in each country:

- a graph showing distribution of PS of the exposed and unexposed pregnancies will be produced and pregnancies with PS in non-overlapping areas will be deleted (trimming).
- based on the trimmed distributions, strata of PS will be defined using boundaries of the gabapentin-exposed pregnancies. Number of strata will be determined by the number of exposed pregnancies and will vary across countries.
- all exposed and unexposed pregnancies included in a given PS estimation will be classified into these strata based on their PS.
- A weight will be assigned to each unexposed pregnancy based on its stratum; each exposed pregnancy will be assigned the weight of 1.
- A weighted regression analysis will be performed, in which adjusted prevalence ratios or adjusted hazards ratios are estimated using a weighted regression model.

Balance of the covariates following trimming and stratifications-strata specific weights will be assessed in each country's dataset using standardised mean differences. Covariates with standardised mean differences <0.1 will be considered balanced. Initially only first-order variables will be entered into the PS models; if imbalance persists, use of interaction terms may be considered. PS will be estimated by an analyst in each country and the final PS models that achieve acceptable covariate balance may be different in each country.

The crude and the adjusted country-specific estimates of association will be reported separately and combined in a meta-analysis (described in [Section 9.7.7](#)).

9.7.4. Primary analyses

The primary analyses will be conducted in the following study population/analysis set: singleton/multiple live births or stillbirths. The assessment of the outcomes stillbirth and major congenital malformations will include stillbirths; the other primary outcomes assessment will exclude stillbirths.

9.7.4.1. Descriptive analysis

- Gabapentin use in pregnancy will be described as the number and proportion of births exposed in the first trimester, and in any trimester. Number and proportion of pregnancies with gabapentin monotherapy will be reported. Cumulative dose during first trimester and any trimester will be described based on the amount of dispensings during a relevant period. Use of pregabalin and lamotrigine will be similarly described.
- Distributions of the characteristics of the study population will be tabulated according to gabapentin exposure categories: first trimester (exposed/unexposed); any trimester (exposed/unexposed) and separately for the monotherapy subgroup. Categorical variables will be summarized using frequencies and proportions; continuous variables using either mean and standard deviation (SD), or median and interquartile range (IQR) as appropriate.
- Distribution of maternal and birth characteristics in the study population will be tabulated according to gabapentin and the active comparator categories, as above. Crude prevalence of the major congenital malformations will be reported according to first-trimester exposure to gabapentin (overall and in the subcategory of monotherapy) and each comparator (overall for all comparators including not exposed and in the subcategory of monotherapy for pregabalin and lamotrigine). In addition, overall prevalence of malformations in the unexposed group will be presented. Crude prevalence of the other birth outcomes (stillbirth, low birth weight, small for gestational age (SGA), preterm birth, low Apgar score at 5 minutes and microcephaly) will be reported according to any trimester exposure to gabapentin and each comparator, in the same fashion.

The defined daily dose (DDD) of gabapentin is 1800 mg.⁵³ In the EU, the recommended/approved daily dose of gabapentin is 900-3600 mg⁵⁴ (equivalent of 0.5-2.0 times the DDD). Three (3) gabapentin cumulative dose (DDD) categories of < 1.0, 1.0-2.0, and > 2.0 times the DDD, will be used to stratify select descriptive analyses of major congenital malformations. The number of major congenital malformation events, the total number of newborns at risk and the prevalence of major congenital malformation events for each of the 3 gabapentin dose categories will be provided. In the study feasibility assessment, even after combining available data from the 4 Nordic countries to obtain a total of 3,298,823 first trimester exposed pregnancies ending in live or still birth, a conservative estimate of 1,592 gabapentin first trimester-exposed pregnancies ending in live or still birth were determined to be available (see Table 3). Given this very small sample size, and the low prevalence of major congenital malformations, it will not be feasible to conduct any extensive stratified analyses (i.e., analyses simultaneously stratified by dose and other variables) or dose dependency analyses. In addition, dose-stratified analyses on the combined dataset will not be possible since data will not be combined at the individual level.

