9.3. Variables

9.3.1. Exposures

For the purposes of identifying timing of exposure, trimesters of pregnancy will be defined as follows:

Gabapentin

A9451182 NON-INTERVENTIONAL STUDY PROTOCOL

Final, 02 October 2020

- First trimester: LMP-90 days to LMP+97 days (both dates inclusive);
- Second trimester: from LMP+98 days to LMP+202 days (both dates inclusive);
- Third trimester: from LMP+203 days (inclusive) until pregnancy end date (not included).

LMP, depending on country is either directly recorded in the birth registry or estimated from gestational age. LMP will be determined using the following hierarchy/availability: ultrasound determined LMP (if recorded), self-reported LMP (if ultrasound-reported is unavailable); date of delivery minus gestational age in days (if LMP unavailable by ultrasound or self-report). If gestational age is missing, LMP will be imputed by subtracting 280 days from date of delivery.

Exposure during the first trimester

Gabapentin exposure during the first trimester is defined as at least one maternal dispensing of gabapentin during the first trimester.

Comparators/reference groups:

No exposure to AEDs-This reference group consists of births with no maternal dispensing of any AED during the first trimester.

Pregabalin exposure in the first trimester is defined by at least one maternal dispensing of pregabalin during the first trimester. Pregabalin monotherapy in the first trimester will be defined as first-trimester exposure to pregabalin and no first-trimester dispensing for any other AED.

Lamotrigine exposure in the first trimester is defined by at least one maternal dispensing of lamotrigine during the first trimester. Lamotrigine monotherapy in the first trimester will be defined as first-trimester exposure to lamotrigine and no first-trimester dispensing for any other AED.

Pregabalin or lamotrigine exposure in the first trimester is defined by at least one maternal dispensing of pregabalin and/or lamotrigine during the first trimester. Pregabalin or lamotrigine monotherapy in the first trimester will be defined as first-trimester dispensing of pregabalin and/or lamotrigine and no first-trimester dispensing for any other AED.

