9.7.4.2. Comparative analysis

Major congenital malformation outcomes

Major congenital malformations (any, each major malformation type, sample size permitting), among pregnancies ending in a live or a stillbirth pregnancy exposed to gabapentin during the first trimester will be compared against each of the comparators estimating crude and adjusted prevalence ratios in log-binomial regression.

In summary, the following comparative analyses will be performed:

- First-trimester gabapentin (monotherapy or polytherapy) vs. first-trimester unexposed to AEDs
- First-trimester gabapentin (monotherapy or polytherapy) vs. first-trimester pregabalin (monotherapy or polytherapy)
- First-trimester gabapentin (monotherapy or polytherapy) vs. first-trimester lamotrigine (monotherapy or polytherapy)
- First-trimester gabapentin (monotherapy or polytherapy) vs. first-trimester pregabalin or lamotrigine (monotherapy or polytherapy)

- First trimester gabapentin (monotherapy only) vs. first-trimester unexposed to AEDs
- First trimester gabapentin (monotherapy only) vs. first-trimester pregabalin (monotherapy only)
- First trimester gabapentin (monotherapy only) vs. first-trimester lamotrigine (monotherapy only)
- First-trimester gabapentin (monotherapy only) vs. first-trimester pregabalin or lamotrigine (monotherapy only)

Prevalence ratios comparing the frequency of major congenital malformations in patients with first-trimester gabapentin exposure (monotherapy or polytherapy) and patients with no first-trimester exposure to AEDs will be estimated within the <1.0, 1.0-2.0, and >2.0 DDD categories; however these estimates are likely to be unstable due to small counts.

Birth outcomes other than major congenital malformations

For birth outcomes other than major congenital malformations, any-trimester gabapentin exposed births will be compared against each of the comparators estimating crude and adjusted prevalence ratios in log-binomial regression.

To summarise, the following comparative analyses will be performed for all outcomes:

- Any-trimester gabapentin (monotherapy or polytherapy) vs. any-trimester unexposed to AEDs
- Any-trimester gabapentin (monotherapy or polytherapy) vs. any-trimester pregabalin (monotherapy or polytherapy)
- Any-trimester gabapentin (monotherapy or polytherapy) vs. any-trimester lamotrigine (monotherapy or polytherapy)

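### Cut-points on the daily-dose scale (1.0 and 2.0 DDD) are applied to cumulative dose, so the gabapentin dose strata would show almost no dose contrast

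*Protocol*

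**What the plan says.** Section 9.7.4.1 gives the reference quantity, "The defined daily dose (DDD) of gabapentin is 1800 mg", and then the labelled range: "the recommended/approved daily dose of gabapentin is 900-3600 mg", put as "equivalent of 0.5-2.0 times the DDD". Both are amounts per day. The next sentence sets the strata: "Three (3) gabapentin cumulative dose (DDD) categories of < 1.0, 1.0-2.0, and > 2.0 times the DDD, will be used". They stratify descriptive tables of major congenital malformations (events, newborns at risk, prevalence).

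The same section says how cumulative dose is obtained: "Cumulative dose during first trimester and any trimester will be described based on the amount of dispensings during a relevant period". Nothing in the protocol text divides that amount by days of supply or by window length.

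The abstract repeats the cumulative-dose strata. The abstract and section 9.7.4.2 also use them comparatively: prevalence ratios against no first-trimester antiepileptic exposure "will be estimated within the <1.0, 1.0-2.0, and >2.0 DDD categories". Section 9.7.4.2 warns that small counts will make these ratios unstable.

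Section 9.7.4.1 adds that "dose-stratified analyses on the combined dataset will not be possible since data will not be combined at the individual level".

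**The concern.** A cut-point has to be on the scale of the variable it divides. Here a boundary suited to an amount per day is placed on a total accumulated over months. Almost any real dispensing passes the upper boundary at once, so the strata would hardly separate low from high exposure.

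The main dose-stratified malformation tables, and the only prevalence ratios by dose, would then show one stratum close to the whole exposed group and two with almost nobody in them. A reader of the report could take the absence of a gradient as evidence about dose, when the strata could not have shown one. The protocol attributes the expected weakness to small counts, but a scale mismatch would persist at any sample size.

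There is also a practical risk. Each country codes its own data (sections 9.6 and 9.7). An analyst who notices the mismatch might silently switch to a daily average, with a denominator of their own choosing, and the four sets of tables would no longer be comparable.

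**Working it through.** **Inputs.** DDD 1800 mg, daily range 900-3600 mg, and the three strata (9.7.4.1). First-trimester window from LMP-90 to LMP+97 inclusive (9.3.1). First-trimester exposed births 1,592: Denmark 374, Finland 374, Norway 344, Sweden 500 (9.5, Table 3). Malformation prevalence 3% (9.5). No data released for fewer than 5 events (9.7). Days supplied per dispensing are not in the protocol, so they are assumed and varied below.

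**1. The protocol's own conversion.** 900/1800 = 0.5 and 3600/1800 = 2.0. The stated range reproduces, in DDD per day.

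**2. Window length.** 90 + 1 + 97 = 188 days.

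**3. What the strata mean on the cumulative scale.** Below 1.0 is less than 1800 mg dispensed in the whole window. Above 2.0 is more than 2 × 1800 = 3600 mg. Days to reach 3600 mg: 3600/900 = 4, 3600/1800 = 2, 3600/3600 = 1.

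**4. Cumulative DDD for assumed supplies** (daily mg × days / 1800):

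| Days supplied | 900 mg/day | 1800 mg/day | 3600 mg/day |
|---|---|---|---|
| 7 | 3.5 | 7 | 14 |
| 30 | 15 | 30 | 60 |
| 90 | 45 | 90 | 180 |
| 188 | 94 | 188 | 376 |

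Every entry is in the top stratum. At 900 mg/day, 5 days gives 2.5 DDD. At an assumed 300 mg/day, below the quoted range, 12 days gives exactly 2.0 and 13 days exceeds it; 30 days gives 5.

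**5. What is left in the lower strata.** Suppose 1-5% of exposed births (assumed) fall in the two lower strata together. That is 1,592 × 0.01 = 16 to 1,592 × 0.05 = 80 births. At 3% this gives 0.5 to 2.4 expected malformations over four countries, and at most 500 × 0.05 × 0.03 = 0.75 in any one country, well under the release limit of 5. At the 5% end the top stratum still holds about 1,512 of 1,592 births and 45.4 of the 47.8 expected events.

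**6. Does dividing by days repair it?** Only with the right denominator.
- Over days covered, 900, 1800 and 3600 mg/day become 0.5, 1.0 and 2.0 DDD/day. The quoted range then spans the two lower strata, and the top stratum means above that range.
- Over the full 188-day window, a 30-day supply at 900-3600 mg/day becomes 15/188 = 0.08 to 60/188 = 0.32, and a 90-day supply 45/188 = 0.24 to 180/188 = 0.96. All fall below 1.0, so the collapse moves to the other end.

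**7. Counts with sound strata.** With equal thirds, expected malformations per third (n × 0.03 / 3) are 3.7 in Denmark, 3.7 in Finland, 3.4 in Norway and 5.0 in Sweden, and 15.9 in total. Three of the four countries expect fewer than 5.

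**The case against.** The scale mismatch itself is hard to defend, but several points limit its reach.

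- **A wording slip.** Section 9.7.4.2 drops the word cumulative, and the daily range stands immediately before the strata, so average daily dose may have been meant. Section 9.3.3 places operational definitions in Annex 3, whose content is not shown, so a denominator there cannot be excluded. This is fair as to intent. The abstract and section 9.7.4.1 still say cumulative, and step 6 shows that the unstated denominator decides where births fall.
- **Unknown dispensing sizes.** A reader might infer that the lower strata are literally empty. The protocol gives no quantities per dispensing, and a few very small dispensings could fall there. Nearly empty, under ordinary supply sizes, is as far as the evidence goes.
- **Other looks at exposure intensity.** A reader might infer that this is the only graded view of exposure. Sections 9.3.2.3 and 9.7.6 also plan a table by one versus more than one dispensing, and cumulative dose is described separately without these cut-points, so that descriptive objective survives. Section 9.7.4.1 itself says dose-dependency analyses are not feasible.
- **Pooling.** A reader might infer that the protocol wrongly forbids combining dose results across countries. The sentence concerns a combined individual-level dataset, which indeed will not exist. Section 9.7.7 pools country estimates for each prespecified comparison, and the dose-stratum ratios are prespecified. The sentence is ambiguous, not wrong. Nor is pooling a full remedy, because the release rule for fewer than 5 events can withhold the very cells to be pooled.
- **Importance.** No main contrast, propensity score or other outcome uses these strata, and the dose ratios are already labelled unstable. This stands and lowers the severity.

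**Conclusion.** The point holds for the dose-stratified malformation analyses. As written, cut-points that fit a daily dose are applied to a total dispensed over 188 days, so the top stratum starts at 1 to 4 days of use at the quoted daily range. If ordinary dispensings cover at least 5 days at 900 mg/day, or at least 13 days at 300 mg/day, nearly all exposed births fall in that stratum, and its prevalence and prevalence ratio largely repeat the overall first-trimester result. The assumption on supply size is the only one needed, and the conclusion is stable over a wide range of it.

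The main comparisons of gabapentin with no antiepileptic exposure, pregabalin and lamotrigine are not touched. It would go too far to say that the dose analyses are empty, that no other graded exposure table is planned, or that the protocol bars pooling of the dose-stratum ratios. Severity: should be fixed. This is a matter of exposure classification only; no clinical dose is judged.

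**What to change.** Reconcile the abstract and sections 9.7.4.1 and 9.7.4.2 on the quantity, its denominator and the matching cut-points. Either of two routes works:

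- **(a) Average daily dose.** Keep 1.0 and 2.0, and define the metric as DDDs dispensed divided by a stated number of days covered. Do not use the full 188-day window as denominator. The cost is an explicit assumption on days covered.
- **(b) Cumulative dose.** Keep the total dispensed and set cut-points on its own scale, for example prespecified tertiles among the exposed, chosen without reference to outcomes. Because patient-level data stay in each country, say whether the boundaries are common or country-specific; country-specific tertiles would not mean the same dose in each country.

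In section 9.7.4.1, clarify that the sentence on the combined dataset rules out only individual-level combined analysis, and that the prespecified dose-stratum prevalence ratios may be pooled under section 9.7.7 where the rule on fewer than 5 events allows release.

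The change costs protocol wording and one derived variable, specified identically for all four countries before extraction. It will not cure the small counts, so the existing caution about instability should stay.

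### The gabapentin 'cumulative dose' categories use cut points taken from a daily dose range, so the dose-specific malformation results would say almost nothing about dose

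*Protocol*

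**What the plan says.** Section 9.7.4.1 describes how dose is measured: "Cumulative dose during first trimester and any trimester will be described based on the amount of dispensings during a relevant period". Nothing there divides the amount by days.

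Later in the same section come three linked statements. "The defined daily dose (DDD) of gabapentin is 1800 mg". The "recommended/approved daily dose of gabapentin is 900-3600 mg", which the protocol gives as the "equivalent of 0.5-2.0 times the DDD". Then: "Three (3) gabapentin cumulative dose (DDD) categories of < 1.0, 1.0-2.0, and > 2.0 times the DDD, will be used to stratify" selected descriptive analyses of major congenital malformations, with events, births at risk and prevalence reported for each category. The abstract repeats this under primary analyses.

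Section 9.7.4.2 and the abstract add prevalence ratios for first-trimester gabapentin against no first-trimester AED exposure, which "will be estimated within the <1.0, 1.0-2.0, and >2.0 DDD categories". The only caution attached to them is that small counts may make them unstable.

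Section 9.3.1 counts a birth as exposed in the first trimester after "at least one maternal dispensing of gabapentin during the first trimester".

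**The concern.** The values 1.0 and 2.0 DDD make sense against a range expressed per day: 2.0 is the top of the quoted range and 1.0 is the DDD itself. The variable being cut is a total over a window of about six months. On that scale both cut points sit near the bottom, where a few days of supply already exceed them.

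Three consequences follow if the text is applied as it stands:

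- The >2.0 category would hold nearly the whole exposed group, so its prevalence and ratio would roughly reproduce the overall first-trimester result.
- That result would carry a label that, in a section equating 2.0 DDD with the top of the approved daily range, could be read as a finding about use above that range.
- Each country codes the variable itself and all must produce identical tables (section 9.7). The wording does not secure one coding, because a total and a daily average can place the same birth in different categories.

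A smaller point concerns the ratios in section 9.7.4.2. They are to be estimated within DDD categories, but births unexposed to AEDs have no gabapentin dose and belong to no category.

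**Working it through.** **Inputs from the protocol.** DDD 1800 mg, daily range 900-3600 mg, and cut points 1.0 and 2.0 DDD (9.7.4.1). First-trimester window from 90 days before to 97 days after LMP, both inclusive (9.3.1). First-trimester exposed births 374, 374, 344 and 500 by country, 1,592 in all (Table 3). Background malformation prevalence 3% (9.5). No release of counts below 5 events (9.7).

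**Assumption.** The documents do not give quantity or days of supply per dispensing. The range tried is 7 to 90 days of supply, plus some small packs.

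**1. The plan's own figure.** 900/1800 = 0.5 and 3600/1800 = 2.0. The stated 0.5-2.0 is exact, as a dose per day.

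**2. The cut points as totals.** 1.0 × 1800 = 1,800 mg and 2.0 × 1800 = 3,600 mg. The window is 90 + 97 + 1 = 188 days. The top cut point is reached after 3600/900 = 4 days at the lowest quoted daily amount, or 3600/3600 = 1 day at the highest.

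**3. One dispensing on that scale.** Cumulative DDD = mg per day × days / 1800.

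| Supply | 900 mg/day | 3600 mg/day |
|---|---|---|
| 7 days | 3.5 | 14 |
| 30 days | 15 | 60 |
| 90 days | 45 | 180 |

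Every entry exceeds 2.0. By pack (assumed sizes): 50 × 100 mg = 2.8 DDD and 100 × 300 mg = 16.7 DDD. Only very small packs stay at or below 2.0, such as 20 × 100 mg = 1.1 and 10 × 300 mg = 1.7.

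**4. What the lower two categories could hold.** Expected events = births × share × 3%, for an assumed share of exposed births at or below 2.0 DDD.

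| Share | Births, all countries | Expected events, all countries | Expected events, per country |
|---|---|---|---|
| 1% | 16 | 0.5 | 0.10-0.15 |
| 5% | 80 | 2.4 | 0.52-0.75 |
| 10% | 159 | 4.8 | 1.03-1.50 |

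To expect 5 events in one country, 5/0.03 = 167 births would have to lie at or below 2.0 DDD. That is 167/500 = 33% of the exposed births in the largest country and 167/344 = 48% in the smallest. For comparison, all exposed births together give 1,592 × 0.03 = 48 expected events, about 10 to 15 per country.

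**5. The alternative reading, an average daily dose.** Take 30 days of supply at 3600 mg a day:

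- as a total: 60 DDD, category >2.0;
- divided by the 188-day window: 60/188 = 0.32, category <1.0;
- divided by the 30 days of supply: 60/30 = 2.0, category 1.0-2.0.

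The same birth can fall in any of the three categories. With the window as denominator, >2.0 needs more than 2 × 188 = 376 DDD dispensed. The cut points span the quoted range only as a dose per day of supply, a denominator the protocol text does not define.

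**The case against.** The strongest reply has four parts.

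- **The intention is guessable.** The categories directly follow a daily range expressed in DDD, so an average daily dose with the wrong label is a plausible reading, and the pile-up in >2.0 need not follow under it. This stands as a reading, but it does not rescue the text: the word cumulative and the definition by amount dispensed would then be wrong, and the denominator would be missing. Operational definitions are referred to Annex 3, whose content is not shown; its visible title mentions only codes.
- **Little rides on it.** The ratios concern one outcome and one comparator and are not among the listed association objectives. The protocol already calls them likely unstable, rules out dose-dependency analyses and will not pool dose strata. This stands and limits the importance of the point. It does not answer it, because the protocol's caution is about small counts, not about a mismatch of scale.
- **The size depends on an outside figure.** This is true of the exact shares. The direction holds over the whole range of supply tried and fails only for very small packs.
- **The reference group is named.** Section 9.7.4.2 does identify births without first-trimester AED exposure as the comparator, so the word within is loose wording and no more.

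A reader might also infer that the dose analyses are empty, or that no birth at all falls in the lower categories. The documents do not support either: the >2.0 category would be full, and small dispensings can stay at or below 2.0.

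**Conclusion.** The scale mismatch is real and is visible in the protocol alone. Cut points from a daily range are applied to a total dispensed over 188 days, so the top one equals 4 days at 900 mg a day or 1 day at 3600 mg a day. If dispensings cover about a week or more, which is an assumption, the two lower categories are near-empty and mostly below the release limit, and >2.0 roughly repeats the overall estimate under a misleading label. If an average daily dose was intended, the variable is mislabelled and its denominator undefined. Either way the text needs correction.

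It would be going too far to conclude that the primary objective of describing use by cumulative dose fails, or that the main results are compromised. That description rests on amounts dispensed and is not tied to these cut points. The main prevalence ratios, the hazard ratios and the pooled estimates do not use the categories. This should be fixed, but it does not threaten the study's principal conclusions.

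**What to change.** Choose one scale and align the abstract (primary analyses), 9.7.4.1 and 9.7.4.2.

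- **(a) Keep cumulative dose.** Set cut points in total DDDs dispensed in the window, identical in all four countries, and fix them before outcomes are examined. Section 9.6 keeps patient-level data from Finland, Norway and Sweden in their own countries, so the cut points have to come from aggregate country-level DDD distributions. Use few categories. With equal division in each country, tertiles give 344/3 × 0.03 = 3.4 to 500/3 × 0.03 = 5.0 expected events per category and country. A median split gives 344/2 × 0.03 = 5.2 to 500/2 × 0.03 = 7.5. The split therefore loses less to suppression, though common cut points will not divide each country evenly.
- **(b) Rename the variable average daily dose.** Keep the cut points and state a denominator that the registries can support, including for women with a single dispensing, who have no refill interval. The documents do not show that days of supply are recorded, so check this first. The 188-day window does not suit these cut points.

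In 9.7.4.2 and the matching abstract text, replace the wording about estimation within categories with a statement that each dose category is compared with the same AED-unexposed group.

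The cost is protocol wording, one recoded variable and, under (a), an exchange of aggregate dose distributions. This concerns analysis categories only and implies nothing about clinical dosing.
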